CLINICAL STUDY PROTOCOL

A Randomized, Open-label Study to compare Propofol Anaesthesia with Sevoflurane Anaesthesia in terms of Overall Survival in Patients with Surgical Intervention for either Breast-, Colon- or Rectal cancer

Study name: CAN

Prospective, randomised, open label, multinational, multicentre study.

Sponsor Project No: CAN / CKF-11115

EudraCT number: 2013-002380-25

Investigational Product: Propofol and sevoflurane

Sponsor: Ass. [name]

Centre of Clinical Research (CKF) Västerås

Västmanland Hospital Västerås [name], SWEDEN

Sponsor Representative: Ass. [name]

Centre of Clinical Research (CKF) Västerås

E-mail: *[contact]* [contact] [contact]

Project Manager, UCR: [name]

Uppsala Clinical Research Center – UCR UCR/MTC, [name]

[name], Sweden

E-mail: [contact]

[contact] [contact]

Coordinating Investigator: Ass. [name], Västerås

The clinical study will be conducted, and essential documentation archived, in compliance with the requirements of the ICH Guideline for Good Clinical Practice.

1 (31)

Clinical Study Protocol CAN version FINAL 2.0
Date: 28 Oct 2016

SYNOPSIS

Name of Sponsor/Company:	Individual study table	(For regulatory authority use
		only)
Name of investigational product:		
Name of active ingredient:		

Title of study:

A Randomized, Open-label Study to compare Propofol Anaesthesia with Sevoflurane Anaesthesia in terms of Overall Survival in Patients with Surgical Intervention for either Breast-, Colon- or Rectalcancer

Investigator(s):

Investigators at up to 20 study centres in Sweden, Poland, Ireland and China. Names and contact details are noted in separate document not included in the protocol.

Study centre(s):

Dept of Surgery/Dept of Anaesthesiology at the study centres.

Planned study period:		Phase of development:
Enrollment:	Q3/2013 – Q4/Q2019	Not applicable
Follow-up period:	Q1/2018 - Q4/2024	

Objectives:

The primary objective is to evaluate whether the one- and five-year survival after radical breast-, or colorectal cancer surgery in general anaesthesia is significantly higher in patients given the intravenously administered hypnotic propofol than in patients given the inhalational hypnotic sevoflurane. The difference is seen as significantly higher and clinically relevant if the absolute difference in five-year-survival is minimum 5%-units.

Methodology:

Prospective, randomised, open label, multinational, multicentre study.

Number of subjects (planned):

8000

Diagnosis:

Patients with surgical intervention for either breast-, colon- or rectal cancer

Inclusion criteria:

- 1. Be informed of the nature of the study and have provided written informed consent
- 2. At least 18 years of age
- 3. Patient that is scheduled for elective radical breast- or colorectal cancer surgery in general anesthesia. Radical surgery means that the aim of the surgery is to cure (adjuvant treatment such as chemotherapy and/or radiation therapy seen as part of the curative treatment).

Exclusion criteria:

- 1. The surgery that is going to be made is an acute surgical procedure
- 2. The surgery that is going to be made is palliative surgery
- 3. Known or suspected hypersensitivity to either propofol or sevoflurane or presence of any contraindication according to the substances' valid SPC
- 4. Lack of suitability for participation in the trial, for any reason, as judged by the Investigator (e.g. communicative disturbances (language or intellectual))

Investigational product, dosage and mode of administration:

Propofol or sevoflurane prescribed and used according to normal clinical practice and in accordance with the Summary of Products Characteristics for the products available on the market for both these substances.

Date: 28 Oct 2016 2 (31)

Name of Sponsor/Company:	Individual study table	(For regulatory authority use only)
Name of investigational product:		only)
Name of active ingredient:		

Duration of treatment:

The hypnotics will be used during the planned surgery.

Active control, dosage and mode of administration:

Not applicable

Criteria for evaluation:

Efficacy:

Not applicable

Safety:

Survival 1 year and 5 year after surgery

Observations made during surgery and up to 365 days post surgery (anaesthesia and surgery related variables)

Statistical methods:

In the present study all endpoints will be evaluated by descriptive methods. All variables will be presented as aggregated data. Categorical variables will be summarised in frequency tables (presenting frequencies and proportions) by type of anaesthesia. The quantitative variables will be summarised by number of observations (n), mean, standard deviation (SD), median, minimum (min) and maximum (max) by anaesthesia. If applicable, separate summaries will be presented for patients receiving one, two or more anaesthesia, as well as pooled summaries. Graphical methods may be used wherever it is regarded as appropriate.

Overall survival (OS) and time to progress (TTP) will be presented as Kaplan-Meier curves together with median survival time and time to progression, respectively.

Clinical Study Protocol CAN version FINAL 2.0

Date: 28 Oct 2016 3 (31)

2 LIST OF ABBREVIATIONS

Abbreviation	Meaning
ALAT	Alanine Aminotransferase
ASA	American Society of Anesthesiologists
ASAT	Aspartate Aminotransferase
BIS	Bispectral Index value
CI	Confidence interval
CKF	Centre of Clinical Research Västerås
CRF / eCRF	Case Report Form / Electronic Case Report Form
CRP	C-reactive protein
DCF	Data Clarification Form
DMP	Data Management Plan
GCP	Good Clinical Practice
ICD	International Classification of Diseases
IEC	Independent Ethics Committee
MAP	Mean arterial pressure
MPA	Medical Products Agency
PI	Principal Investigator
Pts	Patients
RCC	Regional Cancer Centre
SD	Standard deviation
SOP	Standard Operating Procedures
SPC	Summary of Product Characteristics
UCR	Uppsala Clinical Research Centre

Date: 28 Oct 2016 7 (31)

6 BACKGROUND INFORMATION AND STUDY RATIONALE

Centre of Clinical Research Västerås, CKF, is an independent unit connected to both the County Council of Västmanland and the disciplinary domain for medicine and pharmacy at Uppsala University. The Centre focuses on clinical research with aim to improve the standard care. [name] is the Head of CKF until October 2017, thereafter he will be a full time senior researcher.

Inhalational anaesthesia has been gold standard worldwide for long, first with halothane (replacing ether), then isoflurane and enflurane, and later sevoflurane and desflurane. Propofol was introduced in Europe and the USA in late 80's. In few countries, like Belgium, propofol has become the major hypnotic agent, while in most countries, including Sweden; inhalational based anaesthesia has continued to be the main stay.

Based on the data found in literature and a previously completed retrospective study, the Sponsor has a hypothesis that inhalational anaesthetics, which are time- and dose dependently affecting the immune system, and which are also genotoxic, presumably in a dose dependent way, may negatively affect patients' survival after cancer surgery. Theoretically, the opposite may be the case for propofol. This prospective study aims to evaluate whether this hypothesis can be confirmed.

The study will include approximately 8000 patients from up to 20 sites in Sweden, Poland, Ireland and China. The population will be patients that are scheduled for radical breast- or colorectal cancer surgery in general anaesthesia. The patients included in the study will be randomized to either propofol anaesthesia or sevoflurane anaesthesia. Demographic, anaesthesia related, and surgical related variables will be collected. Data about survival will be compiled from the quality registries used within oncology in Sweden. For other countries, there will be local procedures to capture this data.

The study will be completed in accordance with Declaration of Helsinki, Good Clinical Practice (GCP) and applicable regulatory requirements.

6.1 CURRENT STATE OF KNOWLEDGE

6.1.1 IMMUNO-MODULATION

Converging evidence from animal studies and studies of human cell-lines indicate that different anaesthetics have opposite effects on the immune system¹⁻¹⁰. Commonly used inhalational hypnotics, such as isoflurane and sevoflurane, are in this context pro-inflammatory, whereas the intravenously administered hypnotic agent propofol is anti-inflammatory and also anti-oxidative. A few clinical studies have indicated similar effects in patients¹¹⁻¹⁵, and a recent review has suggested that "tailoring an anaesthetic plan to patient's needs will become increasingly critical, and immunology should help in this pursuit"¹⁶.

More specifically, previous studies have investigated the immunological effects of different anaesthetics on monocytes, macrophages, natural killer cells, t-cytotoxic cells, and t-helper cells^{3,5,6,10,15}. By affecting t-helper cells anaesthetics indirectly

Clinical Study Protocol CAN version FINAL 2.0

Date: 28 Oct 2016 11 (31)

affects the production of anti-inflammatory mediators, such as interleukin-4 and -10. Anaesthetics also affect the production of pro-inflammatory cytokines, such as tumour necrosis factor alpha, and interleukin-1 and -6. Moreover, the effects could be indirect by blocking or non-blocking of the surgical stress response via the hypothalamic-pituitary-adrenal axis and the sympathetic nervous system ^{17,18}. Thus, stress hormones, such as catecholamines and cortisol, mediates inhibitory effects on immune functions. In a highly complex way, the neuroendocrine system together with both pro-inflammatory- and anti-inflammatory cytokines augments their immune-suppressive effects. Taken together, results from previous research support that inhalational hypnotics are immune-suppressive in mice^{3,9,19} as well as in humans^{5,6,10}.

Earlier findings also indicate other adverse effects of inhalational hypnotics that could be related to immunological processes. For example, inhalational hypnotics seem to increase the occurrence of cancer metastases^{1,3,19,20}. These adverse effects have not been found for propofol. In contrast, propofol seem to inhibit tumour growth and reduce the tendency to induce metastases^{7,21}.

C-reactive protein (CRP) in blood is a marker of systemic inflammation. Elevated CRP is also a marker of poor cancer prognosis at different sites, including breast- and colorectal²²⁻²⁴. Hence, CRP may be a phenomenological link between the proinflammatory characteristics of inhalational hypnotics to immune-suppression and poorer cancer survival.

The research field of immune-modulation from anaesthetics was recently reviewed by Kurosawa and Kato²⁵. They concluded, that "clinical anaesthesiologists should select anaesthetics and choose anaesthetic methods with careful consideration of the clinical situation and the immune status of critically ill patients, in regard to long-term mortality, morbidity, and the optimal prognosis". A key note is, that "many in vitro investigations have elucidated the dose-dependent and time-dependent immunosuppressive effect of volatile (read inhalational) anaesthetics on various immune cells"²⁵. It was stressed in another review by Meiler, "that the perioperative process could be responsible for later adverse events", and the necessity to "understand the underlying biology and immunology should be particularly helpful in this pursuit"²⁶. Thus, the choice of hypnotic may affect survival after cancer surgery. More specifically, the combined effects of surgical stress and the burden of cancer and perhaps other aggravating circumstances, such as high age and malnutrition, may play a salient role in postoperative morbidity and mortality¹⁶.

There is also other evidence for that anaesthesia may affect survival for patients. [name], now at Duke University (NC, USA), found in a study at University of Florida, Gainesville (FL, USA), involving an unselected cohort of 1,064 patients, that accumulate time in deep anaesthesia (as defined by a Bispectral Index value (BIS) <40¹) was an important independent risk factor for death within one-year²7. In other words, high relative and high absolute doses of anaesthetic drugs were used. Most of their patients (>90%) were anaesthetized with isoflurane, a chemical relative to sevoflurane. Unexpectedly, a majority of the reported mortality was due to malignancies. However, pre-existing malignancies was not controlled for. The authors

Date: 28 Oct 2016 12 (31)

Clinical Study Protocol CAN version FINAL 2.0

¹ BIS (Aspect Medical Systems, Inc., Natic, MA, USA) is based upon a sum of different EEG parameters. Empirically, clinical data has been linked to different index numbers. An index value of 90-100 indicates consciousness, whereas an index value of 40-60 has been recommended as a suitable interval during surgery. An index value <40 is considered as an indicator of unnecessarily deep anaesthetic, i.e. over-dosing.

suggested that, "prolonged deep anaesthesia may alter the inflammatory response in high-risk patients and predispose them to worsened outcomes". Their findings were strengthened by the results in a retrospective Swedish study including 4,087 patients²⁸. Patients with pre-existing malignant diagnoses associated with extensive surgery and less favourable prognosis kept a statistical association with low BIS (read relative over-dose). An inhalational hypnotic, probably sevoflurane, was used for 95% of the patients in the referred study.

Data from a group in Dublin, led by [name], indicate that immune-competence, measured as the intensity for Naural Killer cells, is better preserved in women with breast cancer given a combination of paravertebral block and propofol, than in women given an opioid-sevoflurane combination²⁹. The same group also showed that cancer cell apoptosis is enhanced in patients with breast cancer given the paravertebral-propofol combination compared with patients given the opioid-sevoflurane combination³⁰.

6.1.2 GENOTOXICITY

Genotoxic agents may negatively affect patients' survival after cancer surgery, as the connection between DNA damage and cancer development is well-known. The potential genotoxicity from inhalational anaesthetic agents in patients and in exposed staff in operating rooms has been studied both in vitro^{31,32} and in vivo³³⁻⁴². A doseresponse relationship for inhalational agent exposure and DNA damage has been suggested^{36,37}. The techniques used, the rate of sister chromatid exchange in lymphocytes and the alkaline comet assay, as indicators of genotoxicity are well validated, and they are frequently used in other contexts. Inhalational agents seem to be consistently genotoxic, whereas the less studied propofol seems not to be so ^{38,40}. Some Danish studies could, however, not demonstrate a genotoxic effect from inhalational anaesthetics³⁴. Those studies are most likely inconclusive, since they mainly included short and/or low concentration exposures. It is notable however, that trace exposure of inhalational anaesthetic agents to operating room staff well below the recommended limits in a more recent study induced sister chromatid exchange in non-smokers to the same extent as in persons smoking 11-20 cigarettes per day³³, which indicates that inhalational anaesthetics are potent genotoxic agents.

6.1.3 HYPOXIA-INDUCIBLE FACTOR AND OTHER PROTEINS

Another possible mechanism, however less studied, is the opposing effect on hypoxia-inducible factor (HIF) from different anaesthetic agents, again with a potentially better outcome from propofol⁴³⁻⁴⁶. HIF is a defence factor for tumour growth. As oxygen tension becomes critically low in the peri-necrotic core at the centre of a solid tumour, at a far distance from blood vessels, the level of HIF will increase. A number of adaptive changes will then be mediated by HIF, e.g. angiogenesis and a metabolic shift with pH adaption. Cells, which have adapted most successfully after upregulation of HIF, become more advanced in competing for scarce resources. Such a clone of highly resistant aggressive cancer cells will have heightened ability to invade surrounding tissues and to metastasize. Even when a clear margin of resection is the case during surgery, some marginal cells or micro-metastases may escape removal. As these cells have been exposed to anaesthetics, which by means of interaction with signalling pathways upstream of HIF, the choice of anaesthetic might influence

Date: 28 Oct 2016 13 (31)

[figure not shown]
whether or not, the exposed cells may re-establish a secondary tumour or metastases elsewhere. So far it seems as if inhalational anaesthetics up-regulate HIF, whereas propofol down-regulates this factor⁴³⁻⁴⁶.

There are other proteins of interest for cancer dissemination, e.g. Vascular Endothelial Growth Factor C and Transforming Growth Factor β , which behave differently in breast cancer patients depending on the choice of anaesthesia⁴⁷, again with a potentially better effect from propofol.

6.1.4 DATA FROM RETROSPECTIVE STUDIES

In a retrospective study, "The Choice of Anesthetic and Outcome from Cancer Surgery: A Retrospective Analysis of Surgery for Breast or Colorectal Cancers, Comparing Two Anesthetics", unadjusted data told that survival was higher with propofol anaesthesia, compared with sevoflurane anaesthesia (Fig. 1). However, the retrospective design of this study, with uneven distributions of several confounders and effect modifiers, distorted the picture, so that the statistical significances disappeared after adjustments. The study was found to be under-powered. The p-value for the hazard ratio for sevoflurane was 0.051. Later, a second retrospective study from London, UK, indicated the same result, now with statistical significance⁴⁸.

In-text figure 6-1; Overall survival

Date: 28 Oct 2016 14 (31)

6.2 STUDY TIME TABLE

The patient inclusion will start once the final approval from the IEC and Regulatory Authorities is available.

Preliminary timetable;

3rd - 4th quarter of 2013 First patient in

Time for enrolment 60 months

4th quarter 2018 – 4th quarter 2020* Data compilation, 1 year follow-up Data compilation, 5 year follow-up 2nd quarter 2023-2nd quarter 2025*

7 STUDY OBJECTIVES

We hypothesise that one- and five-year survival after radical breast-, or colorectal cancer surgery in general anaesthesia is 5%-units statistically significant higher in patients given the intravenously administered hypnotic propofol than in patients given the inhalational hypnotic sevoflurane.

The hypothesis is based on:

- 1) The knowledge about the opposite effects on the immune system from the two different forms of anaesthesia and from their different genotoxic potentials.
- 2) The well-established associations between the state of the immune system and cancer growth, and DNA damage and cancer development, with potential influences on survival.

7.1 PRIMARY OBJECTIVE

The primary objective is to evaluate whether the one- and five-year survival after radical breast-, or colorectal cancer surgery in general anaesthesia is significantly higher in patients given the intravenously administered hypnotic propofol than in patients given the inhalational hypnotic sevoflurane.

The difference is seen as significantly higher and clinically relevant if the absolute difference in five-year-survival is minimum 5%-units.

8 **ENDPOINTS**

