8.2 PRIMARY ENDPOINT

The primary endpoint will be a comparison of overall survival using time to event (i.e. death) analysis. Time for death will be collected from the quality registries used within oncology for the Swedish study population. For other countries, there will be local procedures to capture this data.

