14.3 DETERMINATION OF SAMPLE SIZE

A clinically relevant absolute difference in five-year-survival would be 5%-units. Based on data from our retrospective study, we will have 80% power to detect a difference of 5%-units with a *P*-value of <0.05 if including 7,378 patients (see table below). By adding 8.4% more patients to the inclusion of 8,000 patients, we will have a reasonable safety margin for loss of patients or technical errors.

In-text table 14-1– tumor specific sample size calculation:

80% power and 5% significance demands for

Breast cancer with an expected 5-year survival of 87% vs 82% a number of:
Colon cancer with an expected 5-year survival of 60% vs 55% a number of:
Rectal cancer with an expected 5-year survival of 70% vs 65% a number of:
2 728 pts
Margin for loss of patients or technical errors

Total

8 000 pts

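### The 5-point condition for a significantly higher five-year survival equals the effect the trial is powered on, so the 80% power holds for P<0.05 but the condition itself is met only about half the time at that effect

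*Protocol*

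**What the plan says.** Section 7.1 asks whether survival is significantly higher with propofol and then states when that is so: "The difference is seen as significantly higher and clinically relevant if the absolute difference in five-year-survival is minimum 5%-units". The synopsis carries the same sentence. Section 7 merges the same two ideas in the hypothesis, where one- and five-year survival "is 5%-units statistically significant higher in patients given the intravenously administered hypnotic propofol".

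Section 14.3 uses 5 points as the design effect: "A clinically relevant absolute difference in five-year-survival would be 5%-units", and "we will have 80% power to detect a difference of 5%-units" at a P-value below 0.05 with 7,378 patients, raised to 8,000 for losses. The calculation is done separately by tumour type.

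Section 8.2 defines the endpoint differently: "The primary endpoint will be a comparison of overall survival using time to event (i.e. death) analysis". Section 14.2 names no test and confines the evaluation of every endpoint to description, with Kaplan-Meier curves for overall survival.

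**The concern.** A design alternative and a threshold for the result are different things. The first is the true effect at which a test should have good power. The second is a value the estimate has to reach. Here 5 points serves as both. An estimate centred on its own threshold falls short of it about half the time, and adding patients does not help.

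Two things are at stake. A reader of 14.3 would take 80% as the chance of a positive answer to the primary objective if the hypothesis is true, and for the condition in 7.1 that is not so. Also, a significant survival benefit somewhat below 5 points would have no clear status: significant on the test assumed in 14.3, but not significantly higher by 7.1. This matters early, because 14.2 ties further recruitment to the outcome of the breast cancer analysis.

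**Working it through.** **Inputs.** From 14.3: five-year survival of 87% vs 82% (breast), 60% vs 55% (colon) and 70% vs 65% (rectal); 80% power; 5% significance; 2,728 rectal patients; 7,378 in total. From 11.5: 1:1 allocation. Sidedness is not stated. A two-sided test reproduces the sample size; a one-sided two-proportion calculation gives 5,878 and does not.

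**Step 1: reproduce the plan's figure.** Freedman's log-rank formula: events = (1.96 + 0.8416)² × (1 + HR)² / (1 − HR)², with HR = ln p1 / ln p2. N = events / mean five-year death probability.

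- Breast: HR 0.702, 256 events, 256 / 0.155 ≈ 1,652
- Colon: HR 0.854, 1,275 events, 1,275 / 0.425 = 3,000
- Rectal: HR 0.828, 887 events, 887 / 0.325 ≈ 2,730

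The sum is about 7,382, against 7,378 in the plan. A two-proportion formula without continuity correction gives 1,644 + 3,068 + 2,754 = 7,466, within 1.2%. Also 7,378 × 1.084 = 7,998, which matches 8,000. So 14.3 is right for a P<0.05 test.

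**Step 2: cohort sizes.** The breast and colon numbers are unreadable in the text at hand. They must sum to 7,378 − 2,728 = 4,650. Step 1 suggests about 1,650 and 3,000, which are used below as assumptions.

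**Step 3: precision per cohort.** SE = √[(p1q1 + p2q2) / (N/2)], with q = 1 − p.

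| Cohort | N | SE (points) | Significant from (1.96 × SE) | z at an observed 5 points | True difference for 80% chance of observing ≥5 (5 + 0.8416 × SE) |
|---|---|---|---|---|---|
| Breast | 1,650 | 1.78 | 3.5 | 2.8 | 6.5 |
| Colon | 3,000 | 1.80 | 3.5 | 2.8 | 6.5 |
| Rectal | 2,728 | 1.79 | 3.5 | 2.8 | 6.5 |

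For breast, for example: √[(0.1131 + 0.1476) / 825] = 0.0178. An observed 5 points corresponds to a two-sided p of about 0.005.

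**Step 4: chance of meeting the 5-point condition.** P(observed ≥ 5 | true D) = Φ[(D − 5) / SE].

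- D = 4: about 29%
- D = 5: Φ(0) = 50%, whatever the SE
- D = 6: about 71%

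Binomial simulation (400,000 runs per cohort, at the two-proportion sizes) with a true 5 points gave 0.489, 0.502 and 0.506 for observing at least 5 points, and 0.80 in each cohort for P<0.05. The chance of meeting both equalled the first figure, because every run that reached 5 points was also significant.

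**Step 5: pooled.** With 7,378 patients the SE is about 1.09 points and significance starts at 1.96 × 1.09 ≈ 2.1 points. Power for P<0.05 at a true 5 points exceeds 99%, yet the chance of observing at least 5 is still 50%. For 80% the true difference would have to be about 5.9 points.

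**Sensitivity.** Moving the breast N from 1,400 to 1,900 shifts its significance threshold from 3.8 to 3.2 points. The 50% does not move.

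**The case against.** The best defence is that 5 points is only a relevance value. The sentence in 7.1 joins significance and relevance, and 14.3 keeps them apart by calling 5 points clinically relevant and attaching the power to P<0.05. Requiring significance plus a minimum relevant estimate is also a recognised dual criterion. On the relevance-only reading the 80% stands and nothing is miscalculated.

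Part of this holds. The figure in 14.3 is correct for the test it names, and no passage calls a result below 5 points a failure. But the relevance-only reading has to ignore part of the sentence, which makes 5 points the condition for significance as well. If relevance alone was meant, the wording needs correcting. If a dual criterion was meant, its 50% is nowhere disclosed.

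A reader might infer more than the documents support:

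- That the 80% is wrong. It is not; it answers a different question from the condition in 7.1.
- That any significant benefit from 2 points upward would be rejected. An observed 2 points is significant neither in a cohort (about 3.5 needed) nor pooled (about 2.1 needed).
- That 7.1 and 8.2 can disagree in either direction. An observed 5 points has z of about 2.8, so a result that meets the condition but is not significant is not expected at the planned sizes. A five-year difference can also be read from the planned Kaplan-Meier curves, so it does not in itself conflict with a time-to-event endpoint.

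**Conclusion.** The point holds as a conflict between the condition in 7.1 and the synopsis and the power statement in 14.3. At a true difference of 5 points, P<0.05 is reached with probability 80% per cohort and the 5-point condition with probability about 50%. Observed differences of about 3.5 to 4.9 points per cohort (about 2.1 to 4.9 pooled) are significant but fall outside what 7.1 calls significantly higher.

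The 50% assumes that the condition applies to the observed difference and that the truth is exactly the hypothesised 5 points. It depends on no sample size. The per-cohort thresholds also assume the back-calculated breast and colon sizes, a two-sided test, and simple five-year proportions without loss to follow-up. A stricter reading, in which the lower 95% confidence limit must reach 5 points, would bring the chance down to about 2.5%, but nothing in the protocol mentions a confidence limit. The arithmetic is certain; what the sponsor meant by the sentence is not, and that is why the sentence needs rewriting.

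**What to change.** In section 7, section 7.1 and the synopsis, separate the two ideas. Suggested sense: superiority is concluded from the primary time-to-event comparison (for example a log-rank test at two-sided P<0.05, favouring propofol); the five-year survival difference is reported with its 95% CI; 5 points is the design and clinical-relevance value against which that estimate is interpreted, and is not a condition for significance.

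Amend 14.2 to name that test. Without this the change cannot work, because 14.2 as it stands provides only for description.

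If the sponsor prefers to keep 5 points as a joint criterion, leave the 80% in 14.3 for P<0.05 and add that the chance of meeting the joint criterion at a true 5 points is about 50%.

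The cost is a protocol amendment. Because it touches the rule for the primary conclusion in a trial already enrolling, it may count as substantial under section 21.1 and need review by the authorities and the ethics committee. It needs no extra patients or data, and is best settled before the breast cancer analysis.
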